6.2.1.1 Adjuvant chemotherapy

Standard postoperative adjuvant chemotherapy, consisting of a platinum-based doublet for 4 cycles is allowed. For patients receiving adjuvant chemotherapy no more than 26 weeks can elapse between surgery and start of adjuvant capmatinib.

Chemotherapy regimen, dosing, start and stop dates must be recorded in the eCRF.

6.2.1.2 Permitted concomitant therapy requiring caution and/or action

The following medications should be used with caution when concomitantly used with capmatinib treatment in this study:

- **Strong CYP3A inhibitors:** Co-administrating capmatinib with strong CYP3A inhibitor (itraconazole) increased capmatinib AUC_{inf} by 42%. There was no change in capmatinib C_{max} . Closely monitor participants for adverse reactions during coadministration of capmatinib with strong CYP3A inhibitors.
- **Moderate CYP3A inducers:** Simulations using physiologically-based pharmacokinetic (PBPK) models predicted that coadministration of capmatinib with the moderate CYP3A inducer efavirenz (600 mg once daily for 20 days) would result in a 44% decrease in capmatinib AUC_{0-12h} and 34% decrease in C_{max} at steady-state compared to administration of capmatinib alone. Caution should be exercised during concomitant use of capmatinib with moderate CYP3A inducers. Use an alternative medication with no or minimal potential to induce CYP3A during coadministration with capmatinib.
- **Certain CYP1A2 substrates with narrow therapeutic index (NTI):** Capmatinib is a moderate CYP1A2 inhibitor. Coadministration of capmatinib increased sensitive CYP1A2 probe substrate (caffeine) AUC_{inf} by 134%. Avoid coadministration of capmatinib with CYP1A2 substrates where minimal concentration changes may lead to serious adverse reactions. If coadministration is unavoidable, decrease the CYP1A2 substrate dosage in accordance with the approved prescribing information.
- **P-gp and BCRP substrates:** Coadministration of capmatinib increased P-gp substrate (digoxin) exposure (AUC_{inf} and C_{max} by 47% and 74%, respectively) and BCRP substrate (rosuvastatin) exposure (AUC_{inf} and C_{max} by 108% and 204%, respectively). Avoid coadministration of capmatinib with P-gp and BCRP substrates where minimal concentration changes may lead to serious adverse reactions. If coadministration is unavoidable, decrease the P-gp or BCRP substrate dosage in accordance with the approved prescribing information.
- **Proton pump inhibitors:** Coadministration of capmatinib with proton pump inhibitor (rabeprazole) decreased capmatinib AUC_{inf} by 25% and C_{max} by 38%. Exercise caution during concomitant use of capmatinib with proton pump inhibitors.
- **H₂-receptor antagonists and antacids:** As an alternative to proton pump inhibitors, an H₂-receptor antagonist or antacid can be taken. Capmatinib should be administered at least 3 hours before or 6 hours after an H₂-receptor antagonist. Capmatinib should be administered at least 2 hours before or 2 hours after an antacid.

Refer to [Table 16-1](#) for a list of the medications that require caution when concomitantly used with capmatinib. If a medication listed in [Section 16.1](#) appears on both the list of prohibited

and the list of medications to be used with caution ([Table 16-1](#) and [Table 16-2](#)), the medication is prohibited.

6.2.2 Prohibited medication

During the course of the study, participants must not receive other antineoplastic therapies (e.g. investigational drugs, devices, chemotherapy, immunotherapies) or any other therapies that may be active against cancer with exception to adjuvant chemotherapy per [Section 6.2.1.1](#).

Participants enrolled in this study are not permitted to participate in additional parallel investigational drug or device studies while on treatment.

There are no prohibited therapies during the post-treatment follow-up period.

Capmatinib: prohibited medication

Strong CYP3A inducers: Co-administration of capmatinib with strong CYP3A inducer (rifampicin) decreases capmatinib AUCinf by 67% and Cmax by 56% [CINC280A2102], which may decrease capmatinib anti-tumor activity. Therefore, concurrent use of strong CYP3A inducers are prohibited.

Additionally, live vaccines (e.g., intranasal influenza, measles, mumps, rubella, oral polio, BCG, yellow fever, varicella, TY21a typhoid vaccines and COVID 19 vaccines) should not be administered while a participant is on study treatment and for 30 days after the last dose of study treatment.

Capmatinib prohibited medications are listed in [Table 16-2](#).

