Treatment of interest	The treatment of interest and, as appropriate, the alternative treatment to which comparison will be made. These might be individual interventions, combinations of interventions administered concurrently, e.g. as add-on to standard of care, or might consist of an overall regimen involving a complex sequence of interventions. This is the treatment of interest used in describing the related clinical question of interest, which might or might not be the same as the study treatment.

Variable (or endpoint)	The variable (or endpoint) to be obtained for each participant that is required to address the clinical question. The specification of the variable might include whether the participant experiences an intercurrent event.
Victim drug	The drug that is affected by the drug-drug interaction
Withdrawal of study consent (WoC)	Withdrawal of consent from the study occurs only when a participant does not want to participate in the study any longer and does not allow any further collection of personal data

Amendment 1 (17-Mar-2023)

Amendment rationale

[REDACTED]

Additionally, this amendment clarifies the definition of the secondary endpoint, overall response rate (ORR); overall response rate will be based on the best overall response (BOR) by the RECIST 1.1 analysis performed prior to surgery. Since BOR is being determined at the assessment prior to surgery, a confirmatory assessment, 4 weeks later, will not be required, because it is not feasible to delay patient surgery for that reason.

This amendment also includes information that participants should not be receiving live vaccines during treatment or radiotherapy while on study.

The study is currently open at 9 participating sites and 4 patients have been enrolled. This amendment will have no impact on patient safety.

Additional minor protocol language clarifications and updates are made throughout the amendment.

Changes to the protocol

Changes to specific sections of the protocol are shown in track changes version of the protocol using strike through and red font for deletions and red underline for insertions.

- Section 2.1: Updated the variable to clarify evaluable participants.
- Section 3: updated the number of participants with MPR needed to expand a cohort from 1 to 2.
[REDACTED]
- Figure 3-1: Added a footnote indicating adjuvant chemotherapy is optional and at the discretion of the treating physician
[REDACTED].

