- Section 4.5.1: Updated to include most recent safety information
- Section 6.2.1: Clarified that radiotherapy should not be given to participants.
- Section 6.2.2: Added statement that live vaccines should not be administered while participant is on treatment and for 30 days after last dose of treatment.
- Section 6.7.1: Clarified that all unused study treatment should be destroyed at site, when permitted by local regulations and site is able to destroy compliantly.
[REDACTED]
- Section 8.4.5: Added language defining women of childbearing potential.
[REDACTED]
[REDACTED]
[REDACTED]
- Section 9.1.1: Added language to clarify EOT and safety follow up.

- Section 9.2: Clarified study completion definition.
[REDACTED]

- Section 12.4.3: Removed intercurrent events for primary estimand and added intercurrent events for the supplementary estimand.
- Section 12.4.4: clarified that for the primary estimand, only participants with non-missing MPR will be considered for the MPR evaluation and for the supplementary estimands, patients with missing MPR values will be considered non-responders.
- Section 12.5.1: Clarified that best overall response will be determined at the assessments performed prior to surgery. Due to timepoint of assessment, and need for patients to proceed to surgery, there will not be a confirmatory response assessment 4 weeks later.
- Section 12.5.2: Clarified safety follow up is 30 days

Changes to specific sections of the protocol are shown in the track changes version of the protocol using strike through red font for deletions and red underline for insertions.

IRBs/IECs

A copy of this amended protocol will be sent to the Institutional Review Board (IRBs)/Independent Ethics Committee (IECs) and Health Authorities.

The changes described in this amended protocol require IRB/IEC approval prior to implementation.

The changes herein affect the Informed Consent. Sites are required to update and submit for approval a revised Informed Consent that takes into account the changes described in this protocol amendment.

Protocol summary

	CINC280AUS12
Full Title	Phase II trial of neoadjuvant and adjuvant capmatinib in participants with stages IB-IIIA, N2 and selected IIIB (T3N2 or T4N2) NSCLC with MET exon 14 skipping mutation or high MET amplification
Short Title	Geometry-N
Sponsor and Clinical Phase	Novartis
Investigation type	Drug
Study type	Interventional

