6.1.5 Treatment duration

Participants will continue to receive study treatment for a maximum of three years following surgery or until early discontinuation (see [Section 9.1.1](#)). All participants must have an EOT & Safety follow-up visit per the assessment schedule, [Table 8-1](#).

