6.2 Other treatment(s)

6.2.1 Concomitant therapy

In general, the use of any concomitant medications and therapies deemed necessary for the supportive care (e.g. such as anti-emetics, anti-diarrheal) and safety of the participant are allowed except when specifically prohibited (see [Section 6.2.2](#)).

The participant must be told to notify the investigational site about any new medications he/she takes after the start of the study treatment. All medications (excluding study treatment and prior antineoplastic treatments), blood transfusions, surgeries and procedures (including physical therapy) administered within 28 days prior to the first dose administration of study drug through 30 days after the last dose of study drug will be recorded in the Concomitant Medications or Surgical and Medical Procedures eCRF, respectively. Medications include not only physician prescribed medications, but also all over-the counter medications, herbal medications, food supplements and vitamins. In addition, corticosteroid use will be documented on the appropriate eCRF until disease progression (as determined by investigator and confirmed by BIRC). Please refer to [Section 9.2](#).

The following restrictions apply during the entire duration of the study:

- No other investigational therapy should be given to participants
- No anticancer agents other than the study medication should be given to participants with exception to adjuvant chemotherapy per [Section 6.2.1.1](#)
- No radiotherapy should be given to participants

Participants are permitted to use the following medications while taking study drug:

- Oral or topical antibiotics
- Medications to prevent or treat nausea, vomiting or diarrhea
- Oxygen therapy and blood products or transfusions
- Nutritional support or appetite stimulants
- Pain medication

Each concomitant drug must be individually assessed against all exclusion criteria/prohibited medication. If in doubt, the investigator should contact the Novartis medical monitor before enrolling a participant or allowing a new medication to be started. If the participant is already enrolled, contact Novartis to determine if the participant should continue participation in the study.

All medications, procedures and significant non-drug therapies (including physical therapy and blood transfusions) administered after the subject is enrolled into the study must be recorded in the appropriate eCRF.

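### Protocol Section 6.2.2 lists COVID-19 vaccines without qualification as examples of barred live vaccines, so a site reading the list literally could withhold non-live ones (minor wording fix)

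*Protocol*

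**What the plan says.** Protocol Section 6.2.2 (Prohibited medication) carries a vaccine rule that Amendment 1 added. It is directed at live vaccines and gives examples in brackets, the last of which is COVID-19 vaccines with no type or form named: "varicella, TY21a typhoid vaccines and COVID 19 vaccines) should not be administered while a participant is on study treatment". The rule runs on for 30 days after the last dose. The same section also says that nothing is prohibited during post-treatment follow-up.

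Protocol Section 6.2.1 (Concomitant therapy) sets the default. Treatments judged necessary for supportive care and "safety of the participant are allowed except when specifically prohibited", with a cross-reference to 6.2.2. It adds a referral: "If in doubt, the investigator should contact the Novartis medical monitor before enrolling a participant or allowing a new medication to be started".

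Amendment 1 describes the change only in terms of live vaccines. Its rationale says "participants should not be receiving live vaccines during treatment". Its list of changes says "Added statement that live vaccines should not be administered while participant is on treatment and for 30 days after last dose of treatment". Neither mentions COVID-19.

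**The concern.** A list of examples tells the reader what belongs to the class. Here it places COVID-19 vaccines, all of them on its face, in the class of live vaccines that should not be given. A coordinator checking whether a booster is allowed would find COVID-19 vaccines named under the prohibited-medication heading and could stop there.

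What is at stake is participant safety, not inference. Participants have lung cancer, take capmatinib before lung resection, and may take it again afterwards. If the vaccine on offer is not live, withholding it serves no purpose that the rule appears to have.

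**Working it through.** No statistical formula applies. The check sets the relevant texts side by side and then bounds the exposure.

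**1. The two readings of the entry**
- *Narrow.* The rule is about live vaccines, so the entry means any COVID-19 vaccine that is live. The head word and both Amendment 1 descriptions support this.
- *Literal.* The examples are presented as members of the class, so COVID-19 vaccines as a whole are barred. The influenza, polio and typhoid entries each name a particular form, whereas the COVID-19 entry names none.

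**2. Whether other operative text decides between them**
- Section 6.2.1 permits whatever is not specifically prohibited, but it sends the reader back to 6.2.2 to find out what is prohibited. That is circular on this point.
- The referral to the medical monitor works only for a site that is in doubt. A site that sees the vaccine named may have none.
- Table 16-2 (prohibited drugs) lists strong CYP3A4 inducers only.
- Other COVID-19 text covers home delivery of drug (Section 6.1.2), exclusion for active SARS-CoV-2 infection (Section 5.2) and exploration of the pandemic's impact (Section 12.4.3). None of it concerns vaccination.
- The SAP is silent.

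The amendment text is evidence of intent, but it is not the instruction that a site follows. The ambiguity therefore stays open in the operative text.

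**3. The 30-day tail**

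Section 6.2.2 bars the vaccines for 30 days after the last dose, yet says that no therapy is prohibited in post-treatment follow-up. Whether these conflict depends on when follow-up starts:
- In Table 8-1 the follow-up columns hold the end-of-treatment visit and the 30-day safety visit. On that basis the two statements contradict each other for those 30 days.
- In Section 12.5.2 the post-treatment period starts on day 31. On that basis they agree, but that definition is written for the safety analysis.

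**4. Bound on exposure in this trial**

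Inputs:
- Amendment 1 is dated 17-Mar-2023, and its rationale says "The study is currently open at 9 participating sites and 4 patients have been enrolled".
- The final SAP is dated 27-May-2024. Its Document History and Section 4 both give 4 enrolled in total.

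Calculation:
- 17-Mar-2023 to 17-Mar-2024 is 366 days, and 17-Mar-2024 to 27-May-2024 is 71 days.
- 366 + 71 = 437 days, and 437 / 365.25 = 1.2 years per participant.
- 4 × 437 = 1,748 participant-days, and 1,748 / 365.25 = 4.8 participant-years.

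This is an upper limit up to the SAP date. Real exposure is shorter, because Amendment 1 states "The changes described in this amended protocol require IRB/IEC approval prior to implementation", and because time outside treatment and the 30 days after the last dose does not count. It is zero if all four had stopped more than 30 days before their site implemented the amendment. The documents do not say whether anyone was on drug after 27-May-2024.

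**The case against.** The best reply is that the sentence limits itself. It concerns live vaccines, and an example does not normally widen the class it illustrates. Measles, mumps, rubella, yellow fever and varicella also carry no qualifier and take their meaning from the head word. Section 6.2.1 also requires each concomitant drug to be assessed individually and offers a route for questions. The verb is softer than in the antineoplastic rule of the same section, which uses *must not*. Finally, the harm depends on vaccine type, which the documents never give.

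Much of this stands. The narrow reading is the likelier intent, and the safeguard would help a site that hesitates. It does not remove the point. The rule sits under a heading for prohibited medication, names the product, and has no statement elsewhere permitting the non-live form. Vaccine type has to remain a declared assumption.

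A reader might go further in three ways that the documents do not support:
- *That chemotherapy raises the stakes.* Sections 6.2.1.1 and 6.5.1 place adjuvant chemotherapy before capmatinib restarts, so it falls largely outside the time on drug to which the rule applies.
- *That the bar lasted about three years for participants.* Section 6.1.5 does say "Participants will continue to receive study treatment for a maximum of three years following surgery", but all four enrolled before the clause took effect, and their treatment times are not given.
- *That the amendment log and Section 6.2.2 conflict, and that this is the error.* The log is used here only to show intent. A difference between a log and current text is not itself a fault.

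**Conclusion.** The wording defect is real and minor. Taken literally, Section 6.2.2 bars all COVID-19 vaccines during study treatment and for 30 days afterwards. The head word and the amendment suggest that this was not meant, and nothing operative settles it.

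The safety consequence rests on one assumption from outside the documents, that the COVID-19 vaccines offered are not live. If they were live, the entry would be consistent with the rule and no needless withholding would follow. The missing qualifier is visible either way.

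In this trial the effect lies between zero and 1,748 participant-days up to the final SAP. That figure counts calendar time under the clause, not vaccinations missed. It would be wrong to infer that any site misread the rule or withheld a dose, because nothing in the documents shows it. Sample size, endpoints, analysis sets and the planned listings are unaffected.

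**What to change.** Replace the COVID-19 entry in Section 6.2.2 with: *live COVID-19 vaccines, if any; non-live COVID-19 vaccines are permitted*. This is correct whichever type is on offer, so it does not depend on the assumption above.

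In the same edit, reconcile the 30-day bar with the sentence on post-treatment follow-up, either by saying that follow-up in that sentence begins on day 31 or by excepting the vaccine rule from it.

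The cost is one phrase and one clause. Section 14.1 requires a written amendment for any protocol change. If any participant is still on treatment, a letter to sites can clarify the intent in the meantime. If none is, the wording should simply be corrected before it is reused in another protocol.

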6.3 Participant numbering, treatment assignment, randomization

6.3.1 Participant numbering

Each participant is identified in the study by a participant Number (participant No.), that is assigned when the participant is first enrolled for pre-screening and is retained as the primary identifier for the participant throughout his/her entire participation in the trial. The participant No. consists of the Center Number (Center No.) (as assigned by Novartis to the investigative site) with a sequential participant number suffixed to it, so that each participant is numbered uniquely across the entire database. Upon signing the ICF, the participant is assigned to the next sequential participant No. available to the investigator through the Clinical Data Management System interface. Once assigned, the Participant No. must not be reused for any other participant and the Participant No. for that individual must not be changed.

A new ICF will need to be signed if the investigator chooses to re-screen the participant after a participant has screen failed, and the participant will be assigned a new Participant No.

6.3.2 Treatment assignment

Participants will be assigned to a cohort based on their mutational status. All eligible participants will receive treatment with capmatinib.

All participants who fulfill all inclusion/exclusion criteria will be assigned to one of the cohorts of interest and information will be collected.

Cohort A

Cohort A includes eligible participants with MET exon 14 skipping mutations. Participants who have both MET exon 14 skipping mutations and high level MET amplification (MET: GCN ≥ 10 by FISH or FoundationOne CDx NGS using tumor tissue) should be enrolled into Cohort A. Total enrollment to a cohort will depend on the decision to expand the cohort. See [Section 3](#) for the study design.

Cohort B

Cohort B will include eligible participants with high level MET amplification (MET: GCN ≥ 10). Total enrollment to a cohort will depend on the decision to expand the cohort. See [Section 3](#) for the study design.

The study treatment phase begins on Cycle 1 Day 1 with the first administration of capmatinib. Cycle 1 Day 1.

6.4 Treatment blinding

This is an open-label study, therefore treatment assignment will be known to participants, investigator staff, persons performing the assessments, and the Novartis representatives from the Clinical Trial Team.

6.5 Dose modifications

For participants who do not tolerate the protocol-specified dosing schedule, dose interruptions are permitted in order to allow participants to continue the study treatment. All dose modifications, interruptions or discontinuations must be based on the worst preceding toxicity as graded by the NCI Clinical Toxicity Criteria (NCI-CTCAE version 5.0). Any changes must be recorded on the dose administration eCRF page.

Dose reductions are allowed for capmatinib and should follow the dose reduction steps described in [Table 6-2](#) and [Table 6-3](#). For each participant, a maximum of two consecutive dose level reductions is allowed after which the participant must be discontinued. Dose reductions of capmatinib below 200 mg b.i.d are not permitted. The lowest dose allowed, 200 mg b.i.d. in tablets is expected to be pharmacologically active, as the observed steady state plasma trough concentrations ([CINC280X1101], [CINC280X2202], n=6) were above the concentration associated with full MET inhibition in xenograft mice models (IC90, 120 nM total concentration).

A participant must discontinue treatment with capmatinib if, after treatment is resumed at the lowest allowed dose (200 mg b.i.d.), the toxicity recurs with the same or worse severity despite use of maximal preventive measures as per the institution guidelines for toxicity prevention and management.

Unless otherwise indicated in [Table 6-3](#), for grade 1 and tolerable grade 2 treatment-related toxicities, participants may continue full doses of capmatinib. For intolerable grade 2 or grade 3 treatment-related toxicities, dosing should be interrupted until at least resolution to grade 1

followed by either dose reduction or re-initiation at the same dose level, depending on the type of toxicity as described in [Table 6-3](#). For any grade 4 toxicity, except for neutropenia, febrile neutropenia, anemia and thrombocytopenia, participants should interrupt capmatinib until resolution to grade 1, followed by either dose reduction or treatment discontinuation (refer to [Table 6-3](#)).

Permanent treatment discontinuation is mandatory for specific events indicated in [Table 6-3](#). Deviations to mandatory dose discontinuations are not allowed.

All interruptions or changes to study drug administration must be recorded in the dose administration eCRF.

Dose re/escalation of study treatment to previous dose level is allowed only once, and if no AE leading to dose modification is observed after at least 1 cycle (4 weeks) of study treatment at the reduced dose.

Any planned variance from the guidelines in [Table 6-3](#), in view of participant safety (unless there is an urgent need for action) when in the opinion of the investigator the participant continues to experience clinical benefit, should first be discussed and approved by the Novartis Medical Lead or designee.

Events not included in the study protocol or the reference guidance documents should be managed according to local practices. All dose changes must be recorded on the appropriate eCRF.

Table 6-2 Dose reduction steps for capmatinib

	Starting dose level 0	Dose level -1	Dose level -2
capmatinib	400 mg b.i.d	300 mg b.i.d	200 mg b.i.d

Note: dose reduction should be based on the worst toxicity demonstrated at the last dose. Dose reduction below 200 mg is not allowed.

Table 6-3 Criteria for dose reduction / interruption and re-initiation/ permanent discontinuation of capmatinib treatment for adverse drug reactions

Dose modifications for capmatinib	
Worst toxicity CTCAE Grade^a	During a cycle of therapy
No toxicity	Maintain dose level
HEMATOLOGICAL	
Neutrophil count decreased (ANC) Neutropenia	
Grade 1 (ANC < LLN - 1500/mm ³ ; < LLN - 1.5 x 10 ⁹ /L)	Maintain dose level
Grade 2 (ANC < 1500 - 1000/mm ³ ; < 1.5 - 1.0 x 10 ⁹ /L)	Maintain dose level
Grade 3 (ANC < 1000 - 500/mm ³ ; < 1.0 - 0.5 x 10 ⁹ /L)	Omit dose until resolved to ≤ grade 2, then: 
 • If resolved in ≤ 7 days, resume treatment at the same dose level • If resolved in > 7 days, then ↓ 1 dose level

Grade 4 (ANC < 500/mm ³ ; < 0.5 x 10 ⁹ /L)	Omit dose until resolved to ≤ grade 2 and then ↓ 1 dose level
Platelet count decreased (Thrombocytopenia)	
Grade 1 (PLT < LLN - 75,000/mm ³ ; < LLN - 75 x 10 ⁹ /L)	Maintain dose level
Grade 2 (PLT < 75,000 - 50,000/mm ³ ; < 75 - 50 x 10 ⁹ /L)	Maintain dose level
Grade 3 (PLT < 50,000 - 25,000/mm ³ ; < 50 - 25 x 10 ⁹ /L)	Omit dose until resolved to ≤ grade 2, then: 
 • If resolved in ≤ 7 days, then maintain dose level • If resolved in > 7 days, then ↓ 1 dose level
Grade 4 (PLT < 25,000/mm ³ ; < 25 x 10 ⁹ /L)	Omit dose until resolved to ≤ grade 2, then ↓ 1 dose level
Febrile neutropenia (ANC < 1000/mm ³ (< 1.0 x 10 ⁹ /L), fever > 38.3°C)	Omit dose, then: 
 • If resolved in ≤ 7 days, resume treatment at ↓ 1 dose level • If resolved in > 7 days, permanently discontinue participant from study drug treatment
Hemoglobin decreased (Anemia)	
Grade 1 (Hgb < LLN - 10.0 g/dL; < LLN - 6.2 mmol/L; < LLN - 100 g/L)	Maintain dose level
Grade 2 (Hgb < 10.0 - 8.0 g/dL; < 6.2 – 4.9 mmol/L; < 100 - 80 g/L)	Maintain dose level
Grade 3 (Hgb < 8.0 g/dL; < 4.9 mmol/L; < 80 g/L)	Omit dose until resolved to ≤ grade 2, then: 
 • If resolved in ≤ 7 days, resume treatment at the same dose level • If resolved in > 7 days, then ↓ 1 dose level
Grade 4 (Life-threatening consequences; urgent intervention indicated)	Omit dose until resolved to ≤ grade 2 and then ↓ 1 dose level If toxicity recurs, permanently discontinue participant from study drug treatment.
RENAL	
Serum creatinine	
Grade 1 (> ULN - 1.5 x ULN)	Maintain dose level
Grade 2 (> 1.5 - 3.0 x ULN)	Omit dose until resolved to ≤ grade 1 or baseline, then resume treatment at the same dose level.
Grade 3 (> 3.0 - 6.0 x ULN)	Omit dose until resolved to ≤ grade 1 or baseline, then resume treatment at ↓ 1 dose level.
Grade 4 (> 6.0 x ULN)	Permanently discontinue participant from study drug treatment
HEPATIC	
Isolated Total bilirubin elevation*	
Grade 1 (> ULN - 1.5 x ULN)	Maintain dose level

Grade 2 (> 1.5 - 3.0 x ULN)	Omit dose until resolved to \leq grade 1, then: 
 • If resolved in \leq 7 days, maintain dose level • If resolved in > 7 days, \downarrow 1 dose level
Grade 3 (> 3.0 - 10.0 x ULN)	Omit dose until resolved to \leq grade 1, then: 
 • If resolved in \leq 7 days, \downarrow 1 dose level • If resolved in > 7 days, permanently discontinue capmatinib
Grade 4 (> 10.0 x ULN)	Permanently discontinue participant from study drug treatment
Isolated AST or ALT elevation	
Grade 1 (> ULN - 3 x ULN)	Maintain dose level
Grade 2 (> 3.0 - 5.0 x ULN)	Maintain dose level
Grade 3 (> 5.0 - 20.0 x ULN)	Omit dose until resolved to \leq grade 1 (or \leq grade 2 if grade 2 elevation at baseline) then: 
 • If resolved in \leq 7 days, then resume treatment at the same dose level • If resolved in > 7 days, resume treatment at \downarrow 1 dose level
Grade 4 (> 20.0 x ULN)	Mandatory: Permanently discontinue participant from capmatinib treatment
Combined elevations of AST or ALT and Total bilirubin^{b,d}	
For participants with normal baseline ALT and AST and TBL value: AST or ALT > 3.0 x ULN combined with TBL > 2.0 x ULN without evidence of cholestasis ^c Or hemolysis OR For participants with elevated baseline AST or ALT or TBL value: [AST or ALT > 3 x baseline] OR [AST or ALT > 8.0 x ULN], whichever is lower, combined with [TBL > 2 x baseline AND > 2.0 x ULN]	Mandatory: Permanently discontinue participant from study drug treatment
METABOLIC	
Amylase and/or lipase elevation	
Grade 1 (> ULN - 1.5 x ULN)	Maintain dose level
Grade 2 (> 1.5 - 2.0 x ULN; > 2.0 - 5.0 x ULN and asymptomatic)	Maintain dose level
Grade 3 (> 2.0 - 5.0 x ULN with signs or symptoms; > 5.0 x ULN and asymptomatic)	Omit the dose until resolved to \leq grade 2, then 
 • If resolved in \leq 14 days, resume treatment at the same dose level • If resolved in > 14 days, then \downarrow 1 dose level
Grade 4 (> 5.0 x ULN and with signs or symptoms)	Permanently discontinue participant from study drug treatment
CARDIAC	
Electrocardiogram QT corrected (QTc) interval prolonged	
Grade 1 (QTcF 450-480 ms) and	Maintain dose level

Grade 2 (QTcF 481-500 ms)	
Grade 3 (QTcF \geq 501 ms on at least two separate ECGs)	Omit dose until resolved to \leq grade 2, then: 
 • If resolved in \leq 7 days, resume treatment at the same dose level • If resolved in $>$ 7 days, then \downarrow 1 dose level
Grade 4 (QTcF \geq 501 or $>$ 60 ms change from baseline and Torsades de pointes or polymorphic ventricular tachycardia or signs/symptoms of serious arrhythmia)	Permanently discontinue participant from study drug treatment
GASTROINTESTINAL	
Pancreatitis	
Grade 2	Maintain dose level
Grade \geq 3	Permanently discontinue participant from study drug treatment
Diarrhea**	
Grade 1 (despite maximal anti-diarrheal medication)	Maintain dose level
Grade 2 (despite maximal anti-diarrheal medication)	Omit dose until resolved to \leq grade 1, then maintain dose level. 
 • If diarrhea returns as \geq grade 2, then omit dose until resolved to \leq grade 1, then resume treatment at \downarrow 1 dose level
Grade 3 or 4 (despite maximal anti-diarrheal medication)	Omit dose until resolved to \leq grade 1, then resume treatment at \downarrow 1 dose level
Vomiting	
Grade 1 (despite appropriate anti-emetics)	Maintain dose level
Grade 2 (despite appropriate anti-emetics)	Omit dose until resolved to \leq grade 1, then maintain dose level. 
 • If vomiting returns as \geq grade 2, then omit dose until resolved to \leq grade 1, then \downarrow 1 dose level.
Grade 3 (despite appropriate anti-emetics)	Omit dose until resolved to \leq grade 1, then \downarrow 1 dose level
Grade 4 (despite appropriate anti-emetics)	Omit dose until resolved to \leq grade 1, then \downarrow 1 dose level
Nausea	
Grade 1 or 2 (despite appropriate anti-emetics)	Maintain dose level
Grade 3 (despite appropriate anti-emetics)	Omit dose until resolved to \leq grade 1, then \downarrow 1 dose level
SKIN AND SUBCUTANEOUS TISSUE DISORDERS	
Rash/photosensitivity***	
Grade 1	Maintain dose level.
Grade 2	Maintain dose level.
Grade 3, despite skin toxicity therapy	Omit dose until resolved to grade \leq 1, then: 
 • If resolved in \leq 7 days, then resume treatment at \downarrow 1 dose level

	
 • If resolved in > 7 days (despite appropriate skin toxicity therapy), then permanently discontinue participant from study drug treatment
Grade 4, despite skin toxicity therapy	Omit dose and permanently discontinue participant from study drug treatment
RESPIRATORY DISORDERS	
Interstitial Lung Disease (ILD) /Pneumonitis	
	
Monitor participants for pulmonary symptoms indicative of ILD/Pneumonitis. In addition, withhold capmatinib for acute onset of new or progressive unexplained pulmonary symptoms, such as dyspnea, cough and fever and during diagnostic workup for ILD/Pneumonitis to exclude alternative causes such as, but not limited to infections, lymphangitic carcinomatosis, cardiogenic edema, or pulmonary hemorrhage.

Grade 1	
Interrupt capmatinib during diagnostic workup for ILD/Pneumonitis. Exclude infections and other etiologies.
 
In presence of diagnosis of ILD/Pneumonitis after diagnostic workup, it is mandatory to permanently discontinue capmatinib.
 
Only in absence of diagnosis of ILD/Pneumonitis, study drug may be restarted at the same dose.
 
If it recurs after restarting of study drug, permanently discontinue capmatinib.

Grade 2	
Mandatory: Interrupt capmatinib dose during diagnostic workup for ILD until improvement to ≤ Grade 1. Exclude infections and other etiologies.
 
In presence of diagnosis of ILD/Pneumonitis after diagnostic workup, it is mandatory to permanently discontinue capmatinib.
 
Only in absence of diagnosis of ILD/Pneumonitis, study drug may be restarted following these guidelines:
 
 • If resolves to ≤ Grade 1 in ≤ 7 days reduce study drug by 1 dose level • If fails to resolve to ≤ Grade 1 within 7 days or recurs after resumption of study drug at decreased dose, permanently discontinue capmatinib
Grade 3 and Grade 4	
Permanently discontinue study drug
 
Treat with IV steroids as clinically indicated.
 
Oxygen therapy as indicated.

Fatigue/ Asthenia (General disorders and administration site conditions)	
Grade 1 or 2	Maintain dose level
Grade 3	
Omit dose until resolved to ≤ grade 1, then:
 
 • If resolved in ≤ 7 days, resume treatment at same dose level • If resolved in > 7 days, resume treatment at ↓ 1 dose level

Peripheral edema	
Grade 1 or 2	Maintain dose level
Grade 3	Discontinue dose until resolved to \leq Grade 1, then \downarrow 1 dose level
Grade 4	Permanently discontinue study drug
Other AEs	
Grade 1 or 2	Maintain dose level, consider to initiate appropriate support medication. For any intolerable grade 2 (e.g.: limiting instrumental ADL), consider omitting the dose until resolved to \leq grade 1, then restart either at the same dose or \downarrow 1 dose level.
Grade 3	Omit dose until resolved to \leq grade 1, then \downarrow 1 dose level
Grade 4	Permanently discontinue study drug
All dose modifications should be based on the worst preceding toxicity. a Common Toxicity Criteria for Adverse Events (CTCAE Version 5.0). b "Combined" defined as: TBL increase to the defined threshold concurrently with ALT/AST increase to the defined threshold c "Cholestasis" defined as: ALP elevation ($> 2.0 \times$ ULN and R value (ALT/ALP in \times ULN) < 2.0) in participants without bone metastasis, or elevation of ALP liver fraction in participants with bone metastasis d If combined elevations of AST or ALT and TBL do not meet the defined thresholds, please follow the instructions for isolated elevation of TBL and isolated elevation of AST/ALT, and take a conservative action based on the degree of the elevations (e.g. discontinue treatment at the situation when omit dose is needed for one parameter and discontinue treatment is required for another parameter). After all elevations resolve to the defined thresholds that allow treatment re-initiation, re-start the treatment either at the same dose or at one dose lower if meeting a criterion for dose reduction * Note: If TBL $> 3.0 \times$ ULN is due to the indirect (non-conjugated) component only, and hemolysis as the etiology has been ruled out as per institutional guidelines (e.g., review of peripheral blood smear and haptoglobin determination), then \downarrow 1 dose level and continue treatment at the discretion of the investigator. ** Note: antidiarrheal medication is recommended at the first sign of abdominal cramping, loose stools or overt diarrhea *** During the whole duration of treatment with capmatinib, the participant is recommended to use precautionary measures against ultraviolet exposure (e.g., use of sunscreen, protective clothing and avoid sunbathing or using a solarium intensively).	

